## 5.2.2 Dose Modification Guidance

### 5.2.2.1 Dose Modification Sequence by Starting Dose and for General Hematologic and Non-Hematologic Toxicity

Dose reduction guidelines by starting dose and for haematologic and non-haematologic toxicities other than PPE, proteinuria, hypertension, decreased platelet count, hemorrhage, and liver function impairment are shown in [Table 7](#) and [Table 8](#). In principle, treatment should be held until AE/toxicity resolves or improves to  $\leq$ Grade 1. If a Grade 3 toxicity is expected to be manageable and reversible with a dose reduction, treatment should be held until toxicity resolves to  $\leq$ Grade 1. Patients with Grade 3 non-haematologic toxicity that does not resolve to  $\leq$ Grade 1 within 2 weeks should permanently discontinue the study drug.

Patients starting at 5 mg QD are allowed to have two dose reductions: one reduction from 5 mg QD to 4 mg QD, and if not tolerated, then a second reduction from 4 mg QD to 3 mg QD. Patients starting at 3 mg QD are allowed to have 1 dose reduction (ie, from 3 mg QD to 2 mg QD). The lowest dose level permitted in the study is 2 mg (see [Table 7](#)).

**Table 7 Dose Modification Sequence by Starting Dose**

Starting Dose*	3 mg	5 mg
-1 Dose	2 mg	4 mg
-2 Dose	Off study drug	3 mg
	Only 1 dose reduction is allowed for patients starting at 3 mg QD dose.	A maximum of 2 dose reductions is allowed for patients starting at the 5 mg dose.

\* Doses are daily, on Days 1-21 each 28-day Cycle (3 weeks on, 1 week off)

**Table 8 Dose Modification for Hematologic and Non-Hematologic Toxicity**

NCI CTCAE v4.03 Toxicity Grading	Action
Grade 1 or 2 a	None
Grade 3 b	Interrupt the dose until the toxicity resolved to ≤Grade 1 or baseline level within 14 days, then reduce the dose to lower a dose level
Grade 4	Discontinue treatment permanently

a Should any arterial thrombosis occur, the treatment should be terminated.

b Including Grade 3 diarrhea and stomatitis, etc. that are ineffectively treated by drug therapies, but excluding Grade 3 menstrual cycle extension.

### 5.2.2.2 Dose Modification and Treatment Suggestions for Selected Identified Risks

The dose modification and treatment suggestions for specific identified risks are provided in [Table 9](#) (PPE), [Table 10](#) (proteinuria), [Table 11](#) (hypertension), [Table 12](#) (decreased platelet count), [Table 13](#) (hemorrhage at any site), and [Table 14](#) (abnormal liver function).

**Table 9 Dose Modification for PPE**

AE Grading Standard	Dose Adjustment	Treatment Suggestions
Grade 1: numb, paresthesia, dysesthesia, erythema, painless edema, desquamation, thicken skin and hand and foot discomfort which does not affect the normal activities; without any pain	None.	Active supportive treatment can be adopted to relieve the symptoms; for example, moisturizing skin cream, lotion, or hydrophilic urea ointment can be used.
Grade 2: erythema with pain accompanied by hand and foot swelling and /or discomfort, which affects normal activities	The drug could be interrupted; and no dose reduction if the AE recovers to Grade 1 or baseline level within 14 days.	Active supportive treatment can be adopted to relieve the symptoms; for example, moisturizing skin cream, lotion, or hydrophilic urea ointment can be used.
Grade 3: wet desquamation, ulcer, blister or severe hand and foot pain or severe discomfort, which affects work or normal activities.	The drug can be interrupted; the drug should be reduced to a lower dose level if the AE recovers to Grade 1 or baseline level within 14 days.	Active supportive treatment can be adopted to relieve the symptoms; Should the same AE occur for 3 times or still occurs after 2 times of dose reduction, the drug should be terminated.

**Table 10 Dose Modification for Proteinuriaa**

AE Grading Standard	Dose Adjustment	Treatment Suggestions
Grade 1: Proteinuria 1+ by urinalysis;  24-hour urine protein quantitation <1.0 g	None	Follow up at scheduled study visits.
Grade 2: Proteinuria 2+ by the urinalysis;  24-hour urine protein quantitation is between 1.0 to <2.0 g	None	Provide supportive treatment and increase the frequency of urine monitor to once a week; consult nephrologist if necessary.
Grade 2: Proteinuria 2+ or above by urinalysis;  24-hour urine protein quantitation is between 2.0 to <3.5 g (excluding 3.5 g)	The drug can be interrupted and then reduced to lower if the AE recovers to Grade 1 or baseline level within 14 days.	Provide supportive treatment and increase the frequency of urine monitor to once a week; consult nephrologist if necessary.
Grade 3: 24-hour urine protein quantitation ≥3.5 g	The drug can be interrupted and then reduced to lower dose level if AE recovers to Grade 1 or baseline level within 14 days.	Provide supportive treatment and increase the frequency of urine monitor to once or twice a week; consult nephrologist if necessary. Should the same AE occur for 3 times or still occurs after 2 times of dose reduction, the drug should be terminated.

a: If protein ≥ 2+ on urinalysis during the study, a 24-hour urine test should be conducted within 1 week, and dose modification will be done by the result of 24-hour urine protein quantitation.

**Table 11 Dose Modification for Hypertension**

AE Grading and Definitions	Dose adjustment	Treatment Suggestions
Grade 1: prehypertension  (systolic BP 120-139 mmHg or diastolic BP 80-89 mmHg)	None	Follow up as planned schedule
Grade 2: SBP 140-159 mmHg or DBP of 90-99 mmHg; or DBP symptomatic increase >20 mmHg	None	Treatment objective: lower the blood pressure to <140/90 mmHg (or <130/80 mmHg in patients with chronic renal disease and/or diabetes).  Refer to Appendix I .
Grade 3: SBP $\geq$ 160 mmHg or DBP $\geq$ 100mmHg; or more than one drug or more intensive therapy are used	Interrupted once Grade3 hypertension lasting more than 7 days after using or adjusting antihypertensive drug; Should the BP of the patient recover to Grade 1 or the baseline level, one time of dose reduction shall be made.	Treatment objective: lower the blood pressure to <140/90 mmHg (or <130/80 mmHg in patients with chronic renal disease and/or diabetes).  Refer to Appendix I .
Grade 4: Life threatening (eg, malignant hypertension, temporary or permanent neurological deficits and hypertensive crisis)	The drug should be terminated.	Emergent medical treatment.

**Table 12 Dose Adjustment for Decreased Platelet Count**

AE Grading	Dose Adjustment	Treatment Suggestions
Grade 1: Platelet count <LLN - 75,000/ mm  ; <LLN - 75.0 × 10  /L	None	Perform follow up visit as scheduled.
Grade 2: Platelet count <75,000- 50,000/mm  ; <75.0 - 50.0 × 10  /L	Be interrupted and continue the drug treatment with the same dose should the AE recovers to Grade 1 or baseline level within 7 days.	Hematology test should be monitored every 2-3 days; active treatment for platelet elevation is recommended.
	Be interrupted and then reduced to the lower dose level should the AE recovers to Grade 1 or baseline level within 7-14 days.	Hematology test should be monitored every 2-3 days; active treatment for platelet elevation is recommended.
Grade 3: Platelet count <50,000 - 25,000/mm  ; <50.0 - 25.0 × 10  /L	Be interrupted and reduced to the lower dose level should the AE recovered to Grade 1 or baseline level within 14 days.	Hematology test should be monitored every 2-3 days; active treatment (platelet transfusion) to elevate the platelet count is recommended.  Hematology examination should be performed once every week in the follow up visit.
Grade 4: Platelet count <25,000/mm  ; <25.0 × 10  /L	The study drug should be terminated permanently.	Hematology test should be performed once daily until the AE recovers to Grade 2 or a lower grade; platelet transfusion or other active treatment should be provided

**Table 13 Dose Adjustment for Hemorrhage at any Site**

AE Grading	Dose Adjustment	Treatment Suggestions
Grade 1	None	Perform follow up visit as scheduled.
Grade 2	The drug can be interrupted and then reduced to the lower dose level should the AE recovered to Grade 1 or baseline level within 14 days.	Provide Active treatment b
Grade 3 or abovea	The study drug should be terminated permanently.	Emergent medical intervention b

a Refer to [Appendix J](#) for clinical management of severe or serious hemorrhage.

b The investigator should closely monitor patients receiving anti-platelet and/or anti-thrombotic drugs during study drug treatment and make a timely decision on whether to continue or stop such drugs in patients that report Grade ≥2 hemorrhagic events at any site, based on an individual assessment of the risk-benefit balance (See Section 5.3.1 Concomitant therapies).

**Table 14 Dose Adjustment for Abnormal Liver Function**

AE Grading a	Dose Adjustment	Treatment Suggestions
Grade 1	None.	Perform follow-up visit as scheduled.
Grade 2 or 3 (Liver function is abnormal but the biochemical criteria for Hy's Law b are not met)	
 
1. Drug interruption can be considered;
 
2. The dose should be reduced to the lower dose level if the AE recovers to Grade 1 or baseline within 14 days.
 
	Provide supportive care and increase the frequency of liver function monitoring to 1-2 times a week.
Grade 2 or 3 (Liver function is abnormal and the biochemical criteria for Hy's Law b are met)	The study drug should be terminated immediately.	Provide supportive care and increase the frequency of liver function monitoring to 2-3 times a week. Urgent medical intervention indicated.
Grade 4	The study drug should be terminated.	Urgent medical intervention indicated.

a Including increasing of ALT, AST, and total bilirubin, whether or not the biochemical criteria for Hy's Law have been met.

b Hy's Law is an increase in serum AST or ALT  $\geq 3 \times$  ULN together with total bilirubin  $\geq 2 \times$  ULN, and no other reason can be found to explain the biochemical changes, for example, new or worsening hepatobiliary metastases, elevated serum ALP indicating cholestasis, viral hepatitis, another suspect drug, or any other specific cause of severe hepatocellular injury. The elevation in transaminases must precede or be coincident with (ie, on the same day as) the elevation in total bilirubin, but there is no specified timeframe within which the elevations in transaminases and total bilirubin must occur. See Section 7.1.2 for special reporting requirements and Appendix H for additional information regarding Hy's Law.

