### 7.1.3.2 Potential Drug-Induced Liver Injury

The investigator is required to discontinue study drug immediately and report all potential events of drug-induced liver injury (DILI), as defined below, regardless of whether it is a non-serious or serious AE to the sponsor no more than 24 hours after learning of the event.

- Serum AST or ALT  $\geq 3 \times$  ULN together with total bilirubin  $\geq 2 \times$  ULN.

This combination of lab abnormalities meets the biochemical criteria for Hy's law, which is associated with a markedly increased possibility of severe DILI, and may progress to liver transplantation or death. Some patients may present with symptoms such as: fatigue, nausea, vomiting, right upper quadrant pain or tenderness, fever, rash, and/or eosinophilia (>5%). If Hy's law is met, fruquintinib should be immediately discontinued, and patients need to be very closely monitored (bilirubin, ALP, AST, ALT measured 2-3 times weekly until the results return to baseline or normal), and other causes of liver injury evaluated (eg, new or worsening hepatobiliary metastases; non-malignant biliary obstruction; viral hepatitis A, B, or C; alcoholic or autoimmune hepatitis; preexisting or acute liver disease; ischemic liver injury; right-sided congestive heart failure; new or worsening liver metastases; or concomitant medication that could cause the observed injury). Consultation with a gastroenterologist or hepatologist should be considered.

The findings described above must be reported to the sponsor no more than 24 hours after awareness of the event.

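### Table 14 footnote b adds a cause condition and an order condition to a liver stop that Section 7.1.3.2 and Appendix H base on laboratory values alone

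*Protocol*

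**What the plan says.** Protocol Section 7.1.3.2 sets the mandatory rule: "The investigator is required to discontinue study drug immediately and report all potential events of drug-induced liver injury (DILI), as defined below". The definition that follows is AST or ALT ≥3 × ULN with total bilirubin ≥2 × ULN and nothing more. The section adds that "This combination of lab abnormalities meets the biochemical criteria for" Hy's law, and it puts the search for other causes in the follow-up. Appendix H gives the same immediate stop and the same later work-up, with thresholds worded as higher than 3 × and 2 × ULN.

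Table 14 in Section 5.2.2.2 gives the dosing instruction for liver events. Its two Grade 2 or 3 rows are separated by whether the biochemical criteria for Hy's Law are met, and both carry marker b. If they are met, the drug is terminated immediately. If they are not, "Drug interruption can be considered" and then "The dose should be reduced to the lower dose level if the AE recovers to Grade 1 or baseline within 14 days".

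Footnote b defines Hy's Law as the same laboratory pair, "and no other reason can be found to explain the biochemical changes". Its examples include new or worsening hepatobiliary metastases, raised ALP pointing to cholestasis, viral hepatitis and another suspect drug. It then adds: "The elevation in transaminases must precede or be coincident with (ie, on the same day as) the elevation in total bilirubin". The footnote ends with "See Section 7.1.2 for special reporting requirements and Appendix H for additional information regarding" Hy's Law.

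**The concern.** Two parts of one protocol appear to give different stopping conditions for the same laboratory result. Section 7.1.3.2 and Appendix H need only the two values. Table 14, if its trigger is whatever footnote b defines, also needs the absence of another cause and a particular sequence of rises. A patient who has the laboratory pair but fails either added condition would move from an immediate stop to optional interruption and later re-dosing at a lower level. The protocol links this laboratory pattern to severe liver injury that may end in transplantation or death, so the dosing table should not be open to two readings.

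**Working it through.** The plan states no figure on this point, so the check sets the texts side by side and runs cases through them.

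**Step 1. Conditions for the immediate stop.**

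| Text | Laboratory pair (× ULN) | Cause | Order | Action |
|---|---|---|---|---|
| Section 7.1.3.2 | AST/ALT ≥3, bilirubin ≥2 | none; evaluated afterwards | none | stop at once, report within 24 hours |
| Appendix H | AST/ALT >3, bilirubin >2 | none; evaluated afterwards | none | stop at once |
| Table 14 with footnote b, read literally | AST/ALT ≥3, bilirubin ≥2 | no other reason found | transaminases first or same day | met: stop at once; not met: interruption optional, lower dose on recovery |

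**Step 2. Where the pair lands in Table 14.** SAP Appendix 6 gives these CTCAE limits (× ULN):
- AST/ALT: Grade 1 to 3.0, Grade 2 >3.0 to 5.0, Grade 3 >5.0 to 20.0, Grade 4 >20.0.
- Bilirubin: Grade 1 to 1.5, Grade 2 >1.5 to 3.0, Grade 3 >3.0 to 10.0, Grade 4 >10.0.

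Bilirubin at 2 × ULN is therefore already Grade 2, and Protocol Section 5.2.1 applies the highest grade present. A patient with normal baseline values who reaches the pair falls in the split rows. Above 20 × ULN for AST/ALT or 10 × ULN for bilirubin, the Grade 4 row stops the drug whatever the cause.

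Section 5.2.1 also lets the investigator discount a baseline abnormality, so that a move from Grade 1 to Grade 2 is handled as Grade 1. Exclusion Criteria 3 and 4 allow entry with bilirubin up to 1.5 × ULN and, with hepatic metastases, AST/ALT up to 3 × ULN. Both limits are Grade 1, so some patients who reach the pair could be handled outside the split rows.

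**Step 3. Cases, each at ALT 4 × ULN (Grade 2) and bilirubin 2.5 × ULN (Grade 2).**

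| Circumstance | 7.1.3.2 and Appendix H | Table 14, footnote literal | Table 14, labs-only reading |
|---|---|---|---|
| No other cause, ALT first or same day | stop | stop | stop |
| Another suspect drug, ALT first or same day | stop | not-met row | stop |
| No other cause, bilirubin rose first | stop | not-met row | unclear |
| Baseline ALT 3.0 and bilirubin 1.5 × ULN, shift rule used (2 − 1 = 1 grade) | stop | Grade 1 row, no change | Grade 1 row, no change |

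**Step 4. What separates the rows.** In the second case the conflict disappears if biochemical criteria means the laboratory values only. In the third it does not clearly disappear, because the sequence of two laboratory rises is itself a biochemical fact. That patient may already be in the not-met row for the earlier bilirubin rise, and on the literal text stays there when ALT crosses its threshold. The fourth case comes from Section 5.2.1, not footnote b, but the same wording change can close it.

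**Step 5. Cross-references.** Footnote b and Appendix H both cite Section 7.1.2 for reporting, which now covers dose-limiting toxicities. The Amendment 2 history in Appendix K shows that liver injury was then numbered 7.1.2.2, so these are leftover numbers.

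**The case against.** The best answer is that Table 14 does not use Hy's Law as its trigger. It uses the biochemical criteria for Hy's Law, and Section 7.1.3.2 and Appendix H both say that the laboratory combination meets those criteria. Footnote b itself separates the biochemical changes from their explanation and sends the reader to Appendix H. The literal reading also sits badly with an immediate stop: Appendix H's work-up includes hepatitis A to E serology and imaging within 48 hours, so a trigger that waited for it could rarely act at once. Finally, Section 5.2.2.2 introduces its tables with "The dose modification and treatment suggestions for specific identified risks are provided in", whereas Section 7.1.3.2 is phrased as a requirement, and Sections 7.1.3.2 and 7.2 bring the sponsor in within 24 hours.

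Most of this stands, and it largely disposes of the cause clause. It does not dispose of the order clause, which concerns dated laboratory values and can be applied immediately without any work-up. Nor does Table 14 say that either clause lies outside its trigger, and no text ranks Table 14 against Section 7.1.3.2. The terms are not kept apart elsewhere: Section 7.1.3.2 repeats its stop for Hy's law without the word biochemical, and SAP Section 17.4.4 lists ALP <2 × ULN among the components of the biochemical criteria. The SAP does not govern dosing, but it shows that the phrase can be read more broadly than the laboratory pair.

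**Conclusion.** Footnote b is inconsistent with the mandatory stop. The order condition is the part that a careful reader cannot resolve from the text; the cause condition can largely be resolved. This is a minor correction to safety text. The practical conflict needs the laboratory pair below Grade 4 together with another identified cause or a bilirubin-first sequence. The documents give no frequency for any of these, so the number of patients affected cannot be stated.

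A reader might infer more than the documents support:

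- **That the protocol permits continued dosing.** It does not. Section 7.1.3.2 forbids it independently, and the 24-hour report limits the harm if a site misreads the table.
- **That the conflict will be common in a colorectal population with liver metastases.** Footnote b names new or worsening metastases, not existing ones, and progression ordinarily ends treatment under Section 3.6. Exclusion Criterion 26 keeps out active viral hepatitis. The 47.9% for abnormal hepatic function in Table 3 has no grade and does not estimate paired elevations.
- **That every patient with the pair below Grade 4 falls in the split rows.** The baseline-shift rule in Section 5.2.1 prevents that conclusion.
- **That the outdated reference removes the reporting duty.** Sections 7.1.3.2 and 7.2 keep it.

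No endpoint or analysis is affected. SAP Section 17.4.4 identifies potential liver injury by program from laboratory values, and its use of > instead of ≥ is a declared change in SAP Section 2.4.

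**What to change.** In Table 14, state the trigger as: *AST or ALT ≥3 × ULN together with total bilirubin ≥2 × ULN, on laboratory values alone (regardless of cause, order of elevation, or baseline grade shift under Section 5.2.1): stop study drug immediately.* Word the other Grade 2 or 3 row as its complement.

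Add to footnote b: *Alternative causes and the order of the elevations bear only on later adjudication of Hy's Law, not on the immediate stop.*

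As clean-up, change the two Section 7.1.2 references, in footnote b and Appendix H, to Sections 7.1.3.2 and 7.2, and align the Appendix H thresholds to ≥.

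The cost is wording in one table and its footnote, one appendix sentence and two references. It needs no new procedure or data, and no change to the SAP.

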## 5.3 Concomitant and Excluded Therapies

### 5.3.1 Concomitant Therapies

Concomitant therapy includes any prescription medications or over-the-counter preparations used by a patient between the 7 days preceding the screening evaluation and the termination visit. All concomitant medications should be reported to the investigator and recorded on the appropriate CRF.

Patients who use hormonal therapy with GnRH agonists for prostate cancer, oral contraceptives, hormone-replacement therapy, or other allowed maintenance therapy should continue their use.

Prophylactic use of anticoagulation for the maintenance of patency of permanent indwelling central venous access devices or for patients at high risk of venous thromboembolism is permitted during study treatment. If patients are receiving anticoagulation, they should be very closely monitored for potential haemorrhage, and:

- Patients who are receiving warfarin or Coumadin-like products should have their INR monitored and maintained at the lower third of the therapeutic range (ie, 2.0-2.3), unless a higher INR is required for anti-thrombotic efficacy.
- Patients who require low-molecular-weight heparin should receive the prophylactic dose and monitoring as specified by the appropriate product information label.

The investigator should closely monitor patients receiving anti-platelet and/or anti-thrombotic drugs with INR, aPTT and platelet count during study drug treatment and make a timely decision on whether to continue or stop such drugs in patients that report Grade  $\geq 2$  haemorrhagic events at any site, based on an individual assessment of the risk-benefit balance (See [Appendix J](#) for additional information on the clinical management of severe or serious haemorrhagic AEs).

Patients that develop arterial thromboembolic events should discontinue the study drug. If a patient suffers a venous thromboembolic event while still receiving study drug, it may still be possible for him or her to remain on study treatment under close monitoring and dose modification of study drug.

All supportive measures consistent with optimal patient care will be given throughout the study.

### 5.3.2 Excluded Therapies

Any therapy intended for the treatment of cancer (with the exceptions as noted above), whether currently marketed or experimental, is prohibited. This includes, but is not limited to, the following: chemotherapy, hormonal therapy, biologic therapy, radiotherapy, or herbal therapy.

Prophylactic antiemetic, granulocyte colony stimulating factors, granulocyte macrophage colony-stimulating factors, platelet stimulating factors or erythropoietin are not allowed during the DLT observation period in the dose escalation phase.

Concomitant use of acid-reducing agents (eg, proton pump inhibitors, histamine receptor antagonists, antacids) during the dose escalation phase should be avoided as those agents may interfere with identifying reliable MTD and/or RP2D.

Concomitant use of medications that have a known risk of causing QT prolongation and/or torsade de pointes (see “combined” list at <http://www.qtdrugs.org>, with attention to those drugs listed as KR (“known risk”).

Palliative radiation for symptom control is allowed provided it does not compromise tumor assessments of target lesions. However, fruquintinib treatment should be suspended during the radiation period and not resumed until at least 7 days after radiation only after meeting the following criteria:

- Radiation related toxicities resolves to  $\leq$ Grade 2;
- No disease progression observed.

